# 3.0 Animal Studies and Previous Human Studies

The below studies reference 4% ELA-Max cream and EMLA cream. ELA-Max is the former name of L.M.X.4 cream. EMLA cream is similar to the L.M.X.4 cream used by Vanderbilt Pediatric Orthopaedic physicians during routine care tenotomies for pain relief. L.M.X.4 cream is an over the counter medication with an active ingredient of Lidocaine 4%. EMLA cream is a prescription only medication with active ingredients of Lidocaine 2.5%/Prilocaine 2.5%.

Pediatr Emerg Care. 2008 Aug;24(8):511-5. doi: 10.1097/PEC.0b013e31816a8d5b. Jet Injection of 1% buffered lidocaine versus topical ELA-Max for anesthesia before peripheral intravenous catheterization in children: a randomized controlled trial. Spanos S, Booth R, Koenig H, Sikes K, Gracely E, Kim IK.

Abstract

BACKGROUND:

Peripheral intravenous (PIV) catheter insertion is a frequent, painful procedure that is often performed with little or no anesthesia. Current approaches that minimize pain for PIV catheter insertion have several limitations: significant delay for onset of anesthesia, inadequate anesthesia, infectious disease exposure risk from needlestick injuries, and patients' needle phobia.

OBJECTIVE:

Comparison of the anesthetic effectiveness of J-Tip needle-free jet injection of 1% buffered lidocaine to the anesthetic effectiveness of topical 4% ELA-Max for PIV catheter insertion.

METHODS:

A prospective, block-randomized, controlled trial comparing J-Tip jet injection of 1% buffered lidocaine to a 30-minute application of 4% ELA-Max for

topical anesthesia in children 8 to 15 years old presenting to a tertiary care pediatric emergency department for PIV catheter insertion. All subjects recorded self-reported visual analog scale (VAS) scores for pain at time of enrollment and pain felt following PIV catheter insertion. Jet injection subjects also recorded pain of jet injection. Subjects were videotaped during jet injection and PIV catheter insertion. Videotapes were reviewed by a single blinded reviewer for observer-reported VAS pain scores for jet injection and PIV catheter insertion.

#### **RESULTS:**

Of the 70 children enrolled, 35 were randomized to the J-Tip jet injection group and 35 to the ELA-Max group. Patient-recorded enrollment VAS scores for pain were similar between groups (P = 0.74). Patient-recorded VAS scores were significantly different between groups immediately after PIV catheter insertion (17.3 for J-Tip jet injection vs 44.6 for ELA-Max, P < 0.001). Blinded reviewer assessed VAS scores for pain after PIV catheter insertion demonstrated a similar trend, but the comparison was not statistically significant (21.7 for J-Tip jet injection vs 31.9 ELA-Max, P = 0.23). CONCLUSION:

J-Tip jet injection of 1% buffered lidocaine provided greater anesthesia than a 30-minute application of ELA-Max according to patient self-assessment of pain for children aged 8 to 15 years undergoing PIV catheter insertion.

TRIAL REGISTRATION: ClinicalTrials.gov NCT00444756.

Acad Emerg Med. 2018 Mar;25(3):310-316. doi: 10.1111/acem.13351. Epub 2017 Dec 26. A Randomized Double Blind Trial of Needle-free Injected Lidocaine Versus Topical Anesthesia for Infant Lumbar Puncture.

Caltagirone R Raghavan VR, Adelgais K, Roosevelt GE.

# OBJECTIVES:

Lumbar punctures (LPs) are commonly performed in febrile infants to evaluate for meningitis, and local anesthesia increases the likelihood of LP success. Traditional methods of local anesthesia require injection that may be painful or topical application that is not effective immediately. Recent advances in needle-free jet injection may offer a rapid alternative to these modalities. We compared a needle-free jet-injection system (J-Tip) with 1% buffered lidocaine to topical anesthetic (TA) cream for local anesthesia in infant LPs.

METHODS:

This was a single-center randomized double-blind trial of J-Tip versus TA for infant LPs in an urban tertiary care children's hospital emergency department. A computer randomization model was used to allocate patients to either intervention. Patients aged 0 to 4 months were randomized to J-Tip syringe containing 1% lidocaine and a placebo TA cream or J-Tip syringe containing saline and TA. The primary outcome was the difference between the Neonatal Faces Coding Scale (NFCS) before the procedure and during LP needle insertion. Secondary outcomes included changes in heart rate (HR) and NFCS throughout the procedure, difficulty with LP, number of LP attempts, provider impression of pain control, additional use of lidocaine, skin changes at LP site, and LP success.

**RESULTS:** 

We enrolled 66 subjects; 32 were randomized to J-Tip with lidocaine and 34 to EMLA. Six participants were excluded from the final analysis due to age greater than 4 months, and the remaining 58 were analyzed in their respective groups (32 J-Tip, 34 TA). There was no difference detected in NFCS between the two treatment groups before the procedure and during needle insertion for the LP (p = 0.58, p = 0.37). Neither HR nor

NCFS differed among the groups throughout the procedure. Median perception of pain control by the provider and the need for additional lidocaine were comparable across groups. LPs performed with a J-Tip were twice as likely to be successful compared to those performed using TA (relative risk = 2.0; 95% confidence interval = 1.01-3.93; p = 0.04) with no difference in level of training or number of prior LPs performed by providers.

# CONCLUSIONS:

In a randomized controlled trial of two modalities for local anesthesia in infant LPs, J-Tip was not superior to TA cream as measured by pain control or physiologic changes. Infant LPs performed with J-Tip were twice as likely to be successful. TRIAL REGISTRATION:

ClinicalTrials.gov NCT01628874.

J Pediatr Nurs. 2017 Nov - Dec;37:91-96. doi: 10.1016/j.pedn.2017.08.025. Epub 2017 Aug 18. Comparison of Children's Venipuncture Fear and Pain: Randomized Controlled Trial of EMLA® and J-Tip Needleless Injection System®. Stoltz P, Manworren RCB.

# PURPOSE:

Needle procedures, like venipuncture and intravenous (IV) catheter insertion, are recognized as a common cause of pain and fear for children in hospitals and emergency departments. The purpose of this study was to compare children's self-reported pain and fear related to IV insertion with administration of either the topical local anesthetic EMLA® or 1% buffered lidocaine delivered with the J-Tip Needleless Injection System® (J-Tip®).

DESIGN AND METHODS:

In this prospective, randomized trial, 150 consecutive pediatric patients 8 to 18years of age undergoing IV insertion were randomly assigned 1:1 to treatment group. Participants self-reported procedural pain using a Visual Analog Scale, and procedural fear using the Children's Fear Scale.

**RESULTS**:

Procedural pain scores were significantly lower in the EMLA® group (mean score 1.63+1.659) vs. the J-Tip® group (2.99±2.586; p<0.001). Post-procedure fear scores were significantly lower than pre-procedure fear scores in both treatment groups (p<0.002), but there was no difference in fear scores between the two treatment groups (p=0.314). CONCLUSION:

EMLA® provided superior pain relief for IV insertion compared to J-Tip®. PRACTICE IMPLICATIONS:

Although EMLA® use resulted in lower self-reported pain scores compared to J-Tip®, pain scores for both treatments were low and fear scores did not differ. When IV insertion can be delayed for 60-90min, EMLA® should be used. When a delay is contraindicated, J-Tip® may be a reasonable alternative to minimize procedural pain of IV insertion.

# Anesth Analg. 2006 Feb;102(2):411-4.

A comparison of a needle-free injection system for local anesthesia versus EMLA for intravenous catheter insertion in the pediatric patient.

Jimenez N, Bradford H, Seidel KD, Sousa M, Lynn AM.

# Abstract

Placement of IV catheters is a painful and stressful procedure for children. J-Tip is a needle-less Food and Drug Administration approved injection system that can be used for delivery of local anesthetic before IV cannulation. In this study, we compared the effectiveness of J-Tip versus eutectic mixture of local anesthetics (EMLA) to facilitate IV cannulation and provide adequate analgesia before IV placement. Children 7-19 years of age (n = 116) were randomized to receive 0.25 mL of 1% buffered lidocaine with J-Tip (n = 57) or 2.5 g of EMLA (n = 59) before IV cannulation. Measurements of success of cannulation (number of attempts for IV placement) and pain (0-10 visual analog scale) at application of local anesthetic and at cannulation were performed. There was a significant (P = 0.0001) difference in pain ratings during IV cannulation between EMLA (median = 3) and the J-Tip (median = 0). Eighty-four percent of patients reported no pain at the time of J-Tip lidocaine application compared to 61% in the EMLA group at the time of dressing removal (P = 0.004). We did not find differences in the number of attempts for IV cannulation. J-Tip application of 1% buffered lidocaine before IV cannulation is not painful and has better anesthetic effectiveness compared with EMLA.

Study personnel is not aware of any previous studies comparing J-Tip with 1% Buffered Lidocaine to EMLA cream for pain management in infants with clubfoot undergoing a percutaneous Achilles tenotomy.

# 4.0 Inclusion/Exclusion Criteria

Inclusion Criteria

- Clubfoot patients less than 6 weeks of age at start of casting
- Patients presenting to Vanderbilt DOT 4 Clinic for care
- Patients undergoing in-clinic Achilles Tenotomy

**Exclusion** Criteria

- Clubfoot patients greater than 6 weeks of age at the start of casting
- Previous clubfoot treatment
- Patients with a neuromuscular condition (spina bifida, caudal regression syndrome, arthrogryposis, etc.)
- In-office TAL is not recommended by treating physician due to patient factors such as age or size

# 5.0 Enrollment/Randomization

#### **Enrollment**

General inclusion/exclusion criteria will be used to determine patient eligibility for this study. Potential study participants will be identified when they present to the Vanderbilt Children's Orthopaedic or Texas Scottish Rite Hospital for Children clinics for treatment of presumed congenital idiopathic clubfoot.

#### **In-person Consent Process**

When a patient is determined to be eligible for the study, study personnel will approach the patient's parent(s)/legal guardian(s) about taking part in the study. If the patient's parent(s)/legal guardian(s) agree for their child to participate in the study, they will be provided with an informed consent document to review. The consent process will be conducted using either 1) a paper version of the appropriate consent form or 2) a REDCap-based electronic consent form. The electronic consent form has been developed in REDCap, a secure, web-based, HIPAA-compliant, data collection platform with a user management system. The REDCap-based electronic consent form can be accessed by research personnel using any electronic device. They will be given an opportunity to ask questions about the study. If the patient's parent(s)/legal guardian(s) agree for their child to participate in the study by signing the informed consent document, they will be provided with a copy of the signed consent form for their records. Only one parent/legal guardian signature will be required for this study.

#### **Electronic Consent Process:**

In the event a potential study candidate is missed during a clinic visit, or research personnel are unavailable to consent in-person, study personnel will contact the patient's parent(s)/legal guardian(s) by phone to notify them of their child's study eligibility and ask if they would be interested in their child taking part. If the parent(s)/legal guardian(s) are interested in their child taking part in the study, study personnel will send a link to the REDCap-based electronic consent form by e-mail. If the parent(s)/legal guardian(s) agree for their child to take part in the study after reading the informed consent document, there will be an option for one parent/legal guardian to electronically sign their name and date the informed consent document. Once they electronically sign the electronic informed consent document, they will be given an option to save or print the signed electronic informed consent documents for their files.

We will seek to enroll 47 patients per group, 94 patients total in this study at each site.

# **Randomization**

The patients will be randomized in equal proportion (1:1) to either the *control* group (receive L.M.X.4 cream with J-Tip saline injection) or the *intervention* 

*group* (placebo cream with J-Tip with 0.25mL of 1% Xylocaine MPF). Randomization will take place on or after the final casting visit. A randomization allocation table created by statisticians will be uploaded into REDCap. The research coordinator will access the randomization module in REDCap and randomize the participant. Patients will not be randomized until they are definitively diagnosed with congenital idiopathic clubfoot that requires a tenotomy and consented for participation in the study.

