# 6.0 Study Procedures

# Weekly Casting Visits

Once study consent is obtained, the subject will undergo serial casting weekly by one of two board-certified Pediatric Orthopaedic surgeons using the Ponseti method to address their congenital idiopathic clubfoot. CCLS will be present to provide coping support and standardize the environment. This is routine care at our institution. During these castings, patient will wear pulse ox on hand, with mitten covering tool if needed, in order to measure heart rate and oxygen saturation. The CCLS, with assistance from a trained research assistant, will assess the subject's pain and temperament utilizing observational data and data collected from FLACC Scale. Observational assessment is also routine care, but the FLACC data, pulse ox and temperament questionnaire are new, being collected strictly for the study. Primary data will be obtained during casting of first foot and, in the case of bilateral clubfoot patients, a subgroup will be created utilizing data collected during casting of both feet.

Data collection during weekly castings will be obtained by a trained research assistant and will be event based, utilizing pulse ox and FLACC scale. Time points are as follows:

- Baseline before cast placement (patient placed on treatment table)
- Start of casting, after cast padding placed (1st cast if bilateral)
- End of casting (2nd cast if bilateral)

If the subject does not require tenotomy after the weekly casting, they will be withdrawn from the study.

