# Tenotomy

On the day of the subject's tenotomy they will receive pain control based on their group assignment- L.M.X.4 cream (with J-Tip Saline) or J-Tip with 0.25mL of 1% Xylocaine MPF (with placebo cream). The treating physician will provide a Dimeglio score. The following procedures will take place:

- Baseline: FLACC and pulse ox data will be recorded as baby is positioned on treatment table
- Application of randomized topical cream (either L.M.X.4 or placebo cream) for 30 minutes timed.
- Peak FLACC and pulse ox data will be recorded within 5 seconds of application of LMX 4 or Placebo Cream
- Consent for tenotomy procedure will be obtained (routine care).
- Baseline #2: FLACC and pulse ox data will be recorded 30 minutes after cream application
- Parents will leave room (routine care).
- Patient stays with healthcare staff (Physician, nurse, CCLS, cast tech, trained research assistant)
- Cream will be removed from the subject's foot (routine care). Peak FLACC and Pulse Ox will be recorded within 5 seconds after cream removal.
- Baseline #3: FLACC and pulse ox data will be recorded 30 seconds after cream removal
- J-Tip injection with 1% Xylocaine MPF or saline. Peak FLACC scale measurements and pulse ox measurements will be recorded within 5 seconds of injection (1st foot if bilateral)
- Following J-Tip injection there will be a 3-minute break, baby will be calmed during this time.
- Baseline #4: FLACC scale measurements and pulse ox measurements 3 minutes after J-Tip injection
- Tenotomy will be performed
  - FLACC Scale data and Pulse Ox data will be measured during the following events:
    - Percutaneous incision for TAL (1st foot if bilateral)- Peak FLACC scale and Pulse Ox data will be recorded within 5 seconds of poke of scalpel
    - Start of casting, after cast padding placed (1st cast if bilateral)

• End of casting (2nd cast if bilateral)

Adverse local effects of the cream and/or J-Tip injection will be noted (skin redness, swelling, rash, etc). Procedural complications will be recorded (excessive bleeding, concern for neurovascular injury, etc).

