# Data Analysis

FLACC, heart rate, and oxygen saturation will be measured at 10 distinct time points (Table 1) during serial casting and following in-office TAL. Changes in FLACC score, heart rate, and oxygen saturation will be compared between treatment and control cohorts utilizing a two-way ANOVA with a Geisser-Greenhouse correction for matched time measures. A Sidak's multiple comparisons test will be utilized to assess differences between cohorts at each of the 10 time points assessed. To compare number of

complications between cohorts, data will be collected at 3-weeks post TAL and analyzed using a non-parametric Mann-Whitney test, given the ordinal nature of the data. Similar non-parametric analysis with correction for multiple comparisons between cohorts will be utilized to assess changes in responses to REDCap surveys. Statistical analysis will be conducted utilizing GraphPad Prism 8.3.0. Statistical significance will be p<0.05.

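### The planned arm comparisons leave out hospital and laterality, two factors known before randomisation that can affect the outcomes; adjusting for them is a cheap but modest gain

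*Combined protocol and SAP*

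**What the plan says.** **Sites and laterality.** The Enrollment section recruits from the "Vanderbilt Children's Orthopaedic or Texas Scottish Rite Hospital for Children clinics". The Tenotomy section marks injection and incision readings as first foot if bilateral, so infants with one and with two treated feet both take part.

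**Allocation.** The Randomization section says "The patients will be randomized in equal proportion (1:1) to either the" control or intervention group, and "A randomization allocation table created by statisticians will be uploaded into REDCap". No stratification factor, block size or site-specific list is mentioned. On timing: "Randomization will take place on or after the final casting visit", and only after a definitive diagnosis, so hospital and laterality are both known by then.

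**Outcomes.** "Adverse local effects of the cream and/or J-Tip injection will be noted", as are procedural complications, with no per-foot rule. The REDCap surveys ask parents about the child's pain, irritability and Tylenol doses, not about each foot. The end-of-casting reading is taken at the second cast if bilateral.

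**Analysis.** The Data Analysis section compares changes in FLACC, heart rate and oxygen saturation "utilizing a two-way ANOVA with a Geisser-Greenhouse correction for matched time measures", followed by Sidak comparisons between arms at each of 10 time points. Complications are compared by a Mann-Whitney test and the surveys by similar non-parametric tests. Hospital and laterality appear in none of these.

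**The concern.** An infant with two treated feet has two places where a local effect or complication can occur, and the parent gives one rating for a child with two operated feet. The last casting reading also follows a longer procedure in that infant. FLACC is scored by an observer, and the trial runs at two hospitals, so scoring levels may differ between them.

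If the arms happen to differ in their share of bilateral infants, or in their mix of hospitals, part of an observed difference reflects that mix. Complications bear directly on Aim 2. Even with balanced arms, ignored between-hospital variation stays in the error term of between-infant contrasts and makes them less precise. The plan has no safeguard in the analysis, and does not say whether it has one in the allocation.

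**Working it through.** **Inputs from the plan.** 47 per group (Power Analysis; Enrollment). The Enrollment section adds that 94 is the total at each site, which read literally gives 188 infants, or 94 per arm. SD 4.13 and a meaningful difference of 2.0 FLACC points (Power Analysis).

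**Assumed, because the documents give no figure.** Bilateral share 30% to 50%; per-foot complication risk 5%, 10% or 20%, with feet independent.

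**1. The plan's own figure.** With two-sided alpha 0.05 and power 0.8, n = 2 × (1.96 + 0.84)² × 4.13² / 2.0² gives 67 per group (68 by t-test). One-sided it is 53 (54 by t-test). The stated 47 is not reproduced. That is a separate matter: here the sample size only sets how likely an imbalance is.

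**2. Chance of imbalance if the table is unstratified.** Treat the bilateral counts as two independent Binomial(n, p) variables. The SD of the difference in share is √(2p(1−p)/n), which for n = 47 is 0.095 (p = 0.3) to 0.103 (p = 0.5). A 10-point difference means at least 5 infants at n = 47 (0.10 × 47 = 4.7) and at least 10 at n = 94.

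| Per arm | Difference | p = 0.3 | p = 0.4 | p = 0.5 |
|---|---|---|---|---|
| 47 | at least 10 points | 31% | 34% | 35% |
| 47 | at least 15 points | 9% | 11% | 12% |
| 94 | at least 10 points | 13% | 16% | 17% |

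Holding the arms at exactly equal size (hypergeometric) gives 26%, 29% and 41% for at least 10 points at 47 per arm, and 15%, 14% and 19% at 94 per arm. The percentages jump because counts are whole infants. Taking both models, the range at 94 per arm is about 13% to 19%.

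**3. What an imbalance does to complications.** With per-foot risk r, a bilateral infant has at least one complication with probability 1 − (1 − r)², which exceeds the unilateral risk by r(1 − r). A 10-point imbalance shifts the arm difference by 0.10 × r(1 − r):

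| r | Bilateral risk | Excess | Shift at 10 points | Shift at 20 points |
|---|---|---|---|---|
| 5% | 9.75% | 4.75 points | 0.5 points | 1.0 points |
| 10% | 19% | 9 points | 0.9 points | 1.8 points |
| 20% | 36% | 16 points | 1.6 points | 3.2 points |

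In counts, the expected number per infant is r or 2r, so a 10-point imbalance moves the arm difference by 0.10 × r × 47 = 0.24, 0.47 or 0.94 complications per 47 infants.

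**4. Which FLACC contrasts are exposed.** A constant scoring offset between hospitals cancels from within-infant changes and is absorbed by the infant effect in the arm-by-time test. It does not cancel in the Sidak comparisons at each time point, which compare different infants. As an illustration, suppose the offset were as large as 2.0 points and the infants were split evenly between hospitals (both assumed). Its variance would be 0.5 × 0.5 × 2.0² = 1.0, against 4.13² = 17.06, or about 6%. The precision lost is real but modest.

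**The case against.** **No error in allocation is shown.** The table's structure is undescribed, so it may already be stratified. Unstratified 1:1 allocation is valid in any case, and chance imbalance is covered by the type I error rate. This stands: a reader might infer that the trial is biased, or that the arm with more bilateral infants will look worse whatever the drug does, but imbalance can fall either way and averages to zero.

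**Site balance may already be intended.** The Enrollment section's per-site target could mean equal arms within each hospital. It conflicts with the total of 94 in the Power Analysis, so it settles nothing, but the imbalance figures for laterality cannot simply be carried over to site.

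**Laterality matters less for the key pain readings.** Injection and incision FLACC are taken on the first foot. This stands. The end-of-casting reading, complications and surveys remain exposed.

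**The bilateral subgroup proves little.** The plan says that "in the case of bilateral clubfoot patients, a subgroup will be created utilizing data collected during casting of both feet". One might read this as the sponsor expecting laterality to affect complications or parent-reported pain. The sentence sits under Weekly Casting Visits and concerns casting data collected before randomisation, so it does not show that.

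**Not every comparison is affected.** It is tempting to say that site differences inflate the error of every arm comparison. Step 4 shows that they do not.

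**Staffing is not described.** The documents do not say that surgeons, child-life staff or FLACC scorers differ between hospitals. It is a reasonable inference for two hospitals, and no more.

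**Conclusion.** The point holds for the analysis, as a minor improvement. Two factors known before randomisation, each with a plausible route to the outcomes, are absent from every planned comparison, and including them would help precision and guard against chance imbalance. The imbalance itself is not unlikely (31% to 35% for 10 points or more at 47 per arm, about 13% to 19% at 94), provided the table is unstratified and 30% to 50% of infants are bilateral. Its effect on complication risk is small unless complications are frequent: about 0.5 to 1.6 percentage points for a 10-point imbalance. No size can be given for parent-reported pain, because the documents give no figure to work from.

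On allocation, the documents support only that the description is incomplete. They do not show that the table is unstratified.

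**What to change.** Before any unblinded analysis, amend the Data Analysis section in two places, for all infants including those already randomised:

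- Include site and laterality as factors in the arm comparisons of FLACC, heart rate and oxygen saturation.
- Replace the plain Mann-Whitney tests for complications and surveys with a version stratified by site and laterality (van Elteren).

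Also add a sentence to the Randomization section saying how the allocation table is built, including any stratification and blocking.

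**Cost.** Software beyond the planned GraphPad Prism may be needed. The schedule of events does not list laterality by name, so confirm that it is a recorded field. The gain is modest where events are rare.

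Stratifying the remaining allocations is optional and is not the basis of this point. At least 39 patients have already contributed data, so stratification would cover only later infants, and small blocks in four strata would make allocation more predictable to the unblinded coordinator who performs the randomisation. Varying the block size reduces that risk but does not remove it.
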